
Annual Follow-up Visits 24, 36, 48, etc. month post EAS device fitting (visits are projected out (i.e. 96, 144 and 192 weeks, respectively) based on the EAS device activation date +/- 8 weeks)
	
 • Low frequency unaided audiometric testing; unilateral, treated ear • Speech perception testing: Sentence Recognition in Noise – treated ear • Device adjustment / optimization of program parameters if needed to participant's EAS device • Sponsor developed Usability Questionnaires

Termination Visit
	
 • Low Frequency unaided audiometric testing, unilateral, treated ear • Speech perception testing: Sentence Recognition in Noise – treated ear • Sponsor developed Usability Questionnaires

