6.0 Study Objectives

The primary objective of the feasibility study is to evaluate whether *functional* low-frequency acoustic hearing sensitivity can be retained in newly implanted adults with partial deafness (considerable low frequency acoustic hearing profiles with severe-to-profound high frequency sensorineural hearing loss) following the implantation of the HiResolution™ 90K™ Advantage cochlear implant with the HiFocus™ Mid-Scala electrode to further support the development and completion of the Advanced Bionics electro-acoustic stimulation (EAS) technology. Functional hearing is defined as unaided acoustic hearing thresholds (in dB HL) sufficient to be aided with conventional amplification (≤ 80 dB HL). For purposes of this study, the specific criteria to be used is postoperative unaided low frequency audiometric thresholds in the treated ear up to 80 dB HL for at least one frequency from 125-1000 Hz.

There are two groups of study participants that will be recruited for the feasibility study to support the development of electro-acoustic stimulation technology for a partial deafness population: a newly implanted group and an existing implanted group. Each participant group will complete a 12 month test study endpoint visit. Each participant group will have the option to enroll in an EAS Extended Use Arm at the discretion of the managing clinician and the subject. The EAS Extended Use Arm is optional and will provide access to the investigational EAS device up until the point of full commercialization.

Assessment of each participant group (newly and existing implanted groups) will last a minimum of approximately 15-19 months, and will assess the level of residual acoustic hearing (by measurement of audiometric thresholds) and speech understanding performance in the treated ear (and bilateral listening condition) throughout the study.

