7.4 General Subject Population

Projected total study enrollment under this feasibility study is 50 subjects. The Sponsor expects to add to current study recruitment and implant up to an additional 25 adult subjects across 20 study sites in the United States and recruit 15 existing implanted subjects with HiRes90K™ Advantage cochlear implant with HiFocus™ Mid-Scala electrode. The additional 25 subjects for the newly implanted group is additive to the original N=10 subjects (based on initial FDA study approval), thus 35 newly implanted subjects are to be recruited. The existing implanted group of subjects to recruit remains (N=15).

Prior to recruitment, written approval of the investigational plan and informed consent form will be obtained from the FDA and associated participating study center Institutional Review Boards (IRBs). Study participants are required to meet the study inclusion criteria (provided below) as determined by respective medical/hearing care providers. All consented participants meeting

criteria for the newly implanted group will be implanted with the commercially available HiResolution Bionic Ear Cochlear Implant System with the HiRes 90K™ Advantage implant with HiFocus™ Mid-Scala electrode and fit with a currently commercial ear-level (i.e. Naïda family) Advanced Bionics sound processor. A participant's ability to undergo the surgical procedure for cochlear implantation is determined respectively by the participant's managing medical/hearing care providers at his/her implant center. Existing implanted study participants recruited for the study may have been implanted off label on their own accord or through another investigational study.

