- Ability to provide informed consent
- 18 years of age or older, *unilaterally implanted* with HiRes90K™ Advantage cochlear implant with HiFocus™ Mid-Scala electrode and fit with an ear-level sound processor (i.e. Naída family device)
- Postoperative unaided low frequency audiometric hearing thresholds in the treated ear up to 80 dB HL for at least one frequency from 125 – 1000 Hz
- English Language Proficiency
- Willingness to participate in all scheduled procedures outlined in the study protocol

EAS Fitting Exclusion Criteria:

- *Unilaterally implanted* with HiRes 90K™ Advantage cochlear implant with HiFocus™ Helix® and HiFocus™ 1j electrode
- Exclusive use of a body worn external sound processor
- Deafness due to central auditory lesion or cochlear nerve deficiency, diagnosis of auditory neuropathy/dys-synchrony *in either the implanted or the contralateral ear*
- Postoperative unaided low frequency audiometric hearing thresholds in the treated ear exceeding 80 dB HL at each frequency from 125 – 1000 Hz Unwillingness or inability of subject to comply with all investigational requirements as determined by the investigator

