- Unaided air-conduction thresholds using insert earphones at 125, 250, 500, 750, 1000, 1500, 2000, 3000, 4000, 6000 and 8000 Hz; unilateral, each ear
- Unaided bone-conduction hearing thresholds at 250, 500, 1000, 2000, 3000 and 4000 Hz; unilateral, each ear

Note: If the study participant was fit with an AB prototype EAS sound processor, and continues to meet the functional residual hearing criteria (defined as unaided low frequency audiometric hearing thresholds in the treated ear up to 80 dB HL for at least one frequency from 125 – 1000 Hz), he/she should be tested for all aided measures at this study visit using the EAS device.

If the participant was not fit with an AB prototype EAS sound processor (outside EAS fitting inclusion criteria), he/she should be tested using his/her AB commercial (owned) sound processor for all aided test measures at this interval.

If no preserved functional residual acoustic hearing has been previously documented and/or if the participant loses functional residual hearing as defined in the inclusion criteria, the participant should resume use and be tested with his/her AB commercial (owned) cochlear implant sound processor for these study intervals. The investigational EAS device should be returned expeditiously to the managing study site should functional residual hearing be lost.

- Aided soundfield hearing thresholds at 250, 500, 750, 1000, 1500, 2000, 3000, 4000 and 6000 Hz; Treated ear (*Note: Plug and muff method will be used in the ear contralateral to the one being measured here*)

Speech Perception Testing:

Note: The participant's Preferred Listening Program is to be used during speech perception test measures. Participants fit with the AB prototype EAS sound processor should use his/her preferred EAS program; participants not fit with the EAS device should use his/her AB commercial device and preferred CI listening program.

- CNC Word Test (Quiet) – Two Lists of 50 words presented at 60 dBA (Target 0° Azimuth) in the following condition:
 - Unilateral Aided – Treated Ear (*Note: Plug and muff method will be used in the ear contralateral to the one being measured here*)
- AzBio Sentence Test (Noise) – Two lists at 60 dBA with a +5dB SNR using speech spectrum noise (Target/Noise 0° Azimuth) in the following conditions:
 - Unilateral Aided – Treated Ear (*Note: Plug and muff method will be used in the ear contralateral to the one being measured here*)
 - Bilateral Condition

Self-Assessment Questionnaire(s):

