The study participant should be tested for all aided measures at this study visit using the EAS device.

Note: If an existing implanted participant loses functional residual hearing during the study (outside the EAS fitting inclusion criteria), the prototype EAS device should be removed and returned to the managing study center. The participant should resume use of his/her commercial (owned) cochlear implant sound processor. The study subject's participation in the feasibility will end at the respective test interval respectively.

Aided soundfield hearing thresholds at 250, 500, 750, 1000, 1500, 2000, 3000, 4000 and 6000 Hz; Treated ear (Note: Plug and muff method will be used in the ear contralateral to the one being measured here)

Speech Perception Testing:

Using the AB prototype EAS sound processor and Preferred EAS Listening Program, please test the following speech perception measures/conditions:

- CNC Word Test (Quiet) – Two Lists of 50 words presented at 60 dBA (Target 0° Azimuth) in the following condition:
 - Unilateral Aided – Treated Ear (Note: Plug and muff method will be used in the ear contralateral to the one being measured here)
- AzBio Sentence Test (Noise) – Two lists at 60 dBA with a +5dB SNR using speech spectrum noise (Target/Noise 0° Azimuth) in the following conditions:
 - Unilateral Aided – Treated Ear (Note: Plug and muff method will be used in the ear contralateral to the one being measured here)
 - Bilateral Listening Condition

Self-Assessment Questionnaire(s):

- Speech, Spatial and Sound Qualities (SSQ-B* / Standard Questionnaire)
- Abbreviated Profile of Hearing Aid Benefit (APHAB)
- Sponsor developed Patient Report Form
- Sponsor developed Usability Questionnaire

**Note: The SSQ-B is administered at the 3 and 6 month test intervals; standard version administration at the 12 month test interval visit.*

Device Optimization-Re-Programming:

Adjustment/optimization of participant's AB commercial and/or prototype EAS device program parameters as needed or recommended by managing clinician.

EAS Extended Use Arm - Annual Follow-up Visits:

Each participant completing the 12 Month EAS Device Fitting Visit will have the option to enroll in the EAS Extended Use Arm with annual follow-up. Enrollment is optional and subject to the willingness of the participant and the discretion of the managing clinician. The EAS Extended Use Arm, with annual follow-up, shall continue up until the point of full commercialization of EAS.

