 - Leakage of inner ear fluid or cerebrospinal fluid which may increase the risk of meningitis. Meningitis is an infection in the fluid and tissue that surround the brain and spinal cord. There are two types viral and bacterial meningitis; bacterial being the most serious type and has been reported in cochlear implant recipients. The Centers for Disease Control (CDC) recommends for patients pursuing cochlear implantation to be up to date on age-appropriate pneumococcal vaccination. More information about the CDC recommendations can be found at <http://www.cdc.gov> or by calling [name]. It is recommended to discuss vaccinations and surgical risks with the subjects prior to the scheduled procedure.
 - Hearing may sound different when the cochlear implant is turned on
- Risks associated with implantation of the internal cochlear implant device and electrode array
 - The presence of a foreign body (implant) may result in irritation
 - Redness or breakdown of the skin in the area around the implant receiver/stimulator and/or rejection of the device
 - The electrode array may migrate partially resulting in reduced hearing ability
 - Misplacement of the electrode array may result in non-auditory sensations which may require additional medical treatment, surgery and/or removal of the device, however, this is considered a rare circumstance
 - Electrical stimulation may increase tinnitus, facial nerve stimulation, balance related issues (i.e. dizziness, vertigo) or pain

- Implantation in the cochlear may preclude the use of future implant technology
- Device failure of operation that may perhaps require removal of the device
- Newly Implanted and Existing Implanted Group Participants
 - Overall risks of being fit with and using prototype external sound processor systems are considered no greater than those associated with the commercial external sound processor system in general
 - Choking hazard due to small parts/pieces of the device
 - Residual natural hearing damage if programming error or sound overstimulation
 - Uncomfortable hearing sensation or overly-loud sound due to hardware malfunction
 - Irritation of skin with prototype device
 - Neural tissue damage due to chronic overstimulation
 - Device malfunction or explant due to exposure to high levels of static electricity and electric shock due to non-isolated conduction paths when connected to medical equipment

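### Existing-group participants who lose functional hearing leave the study at that visit, so the group's 12-month summaries are largely conditional on hearing retained

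*Combined protocol and SAP*

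**What the plan says.** Entry to the existing group requires an unaided threshold "in the treated ear up to 80 dB HL for at least one frequency" between 125 and 1000 Hz (Section 7.5; repeated in Section 9.2). At 3, 6 and 12 months Section 9.2 directs: "The study participant should be tested for all aided measures at this study visit using the EAS device". A note there covers later loss. It begins "If an existing implanted participant loses functional residual hearing during the study (outside the EAS fitting inclusion criteria"), provides for device return and resumption of the commercial processor, and concludes that "participation in the feasibility will end at the respective test interval respectively".

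Other sections read differently:

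- Section 9.1, newly implanted group, same event: "the participant should resume use and be tested with his/her AB commercial (owned) cochlear implant sound processor for these study intervals". Follow-up continues.
- Section 6.0, both groups: "Each participant group will complete a 12 month test study endpoint visit". It also says adverse events are tracked through the 12-month visit.
- Table 3 marks the existing group's 12-month interval as required and shows no exit.
- Section 9.4 describes device return after loss in this group and does not mention ending participation.
- Section 7.6 lists reasons for discontinuation. Hearing loss is not among them.

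Section 10.0 plans counts of participants who improve, do not change or decline. Section 11.0, item 4, plans evaluation of both groups after EAS fitting and over chronic use, with contralateral thresholds as an example. Neither says how to handle participants who exit under Section 9.2.

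**The concern.** Follow-up in this group ends because of the outcome being measured. A participant whose low-frequency hearing falls below the criterion at 1, 3 or 6 months contributes nothing at month 12. The 12-month thresholds, speech scores and questionnaires then come from a group selected twice on hearing: at entry and again during follow-up.

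Section 12.1 lists "Residual natural hearing damage if programming error or sound overstimulation" as a risk of the investigational external device for both groups. Existing participants enter already implanted, so a loss after EAS fitting is less mixed up with the effect of surgery than it is in the new group. After such a loss the plan collects no later thresholds in either ear, so progression or recovery is not seen. Section 4.0 says the study should inform device safety and the choice of pivotal-study endpoints. Figures from retained participants, read as figures for the group, would mislead that use.

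**Working it through.** **The plan's own figure.** Section 7.4: 10 + 25 = 35 newly implanted; 35 + 15 existing = 50. This adds up. No hypothesis, alpha, power or dropout rate is stated, so there is no sample-size formula to reproduce.

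**What is missed.** The visits are at 1, 3, 6 and 12 months. Exit at month 1 loses three scheduled visits, exit at month 3 loses two, exit at month 6 loses one, and a loss first found at month 12 loses none.

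**What is still captured.** Section 9.2 lists unaided thresholds first at each visit, ahead of the exit note, so the loss is measured. It can also be recorded as an adverse event. Collection then stops two weeks after the last visit (Section 12.1), unless the loss is classed as a device-related AE or an SAE (Sections 7.6 and 12.1). The audiometric SAE trigger in Section 12.1 (50 dB or more at two or more frequencies) is written for newly implanted participants only. For the existing group, the extension therefore rests on how the investigator classifies the event.

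**Size.** Let n = 15 (Section 7.4), k = exits for hearing loss before month 12, and D = mean threshold difference in dB, those who exit minus those who stay. The documents give neither k nor D, so both are assumptions. Other dropout is ignored.

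- Retention over all fitted participants = (15 − k)/15, with exact Clopper-Pearson limits. Among 12-month attendees it is (15 − k)/(15 − k).
- If stayers have mean m, the mean over all 15 is [(15 − k)m + k(m + D)]/15 = m + kD/15. The attendee mean is therefore too favourable by kD/15.

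| k | Attendees | All fitted (exact 95% CI) | kD/15 for D = 20 to 40 dB |
|---|---|---|---|
| 1 | 14/14 | 14/15 = 93% (68-100%) | 1.3 to 2.7 dB |
| 3 | 12/12 | 12/15 = 80% (52-96%) | 4.0 to 8.0 dB |
| 6 | 9/9 | 9/15 = 60% (32-84%) | 8.0 to 16.0 dB |

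**Chance that it arises.** P(at least one early exit) = 1 − (1 − p)^15. For assumed loss risks of 10%, 20% and 30% this is 79%, 96.5% and 99.5%, with 1.5, 3 and 4.5 exits expected.

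**The case against.** The strongest reply is that the two groups answer different questions. In the new group implantation is under evaluation, so follow-up after loss is informative. In the existing group the study adds only the external EAS device, to learn about integration, sound quality and preference (Section 6.0). Later aided scores with a processor already tested at baseline would say little about EAS. This stands for aided speech testing. It does not cover unaided thresholds, contralateral monitoring or adverse events.

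A second reply is that Section 6.0 is an overview and Section 9.2 a specific exception. That is a fair reading, but Table 3 and Sections 7.6 and 9.4 do not carry the exception, and no reason for it is given.

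A reader might go further and infer that losses vanish, or that EAS safety is judged from survivors alone. The documents do not support that. The loss is measured at the exit visit, Section 7.6 requires each participant's disposition to be logged, and Section 12.2 bases adverse-event percentages on all subjects. Nor can one infer that safety follow-up always stops at two weeks, given the extensions in Sections 7.6 and 12.1. Nor does the plan commit to a 12-month retention percentage for this group: 12/12 is a figure the data would invite, not one the plan specifies.

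**Conclusion.** The point holds with moderate severity. The exit rule depends on the outcome, conflicts with other sections, and is not offset by any analysis rule. Apart from losses first found at month 12, which still contribute that visit's unaided thresholds, the existing group's 12-month summaries are conditional on 80 dB HL or better at one or more frequencies from 125 to 1000 Hz. That criterion is lenient, so those who stay may also have lost considerable hearing. Post-loss course is what goes missing, not the loss event.

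The numerical size rests on assumed values of k and D. It would be too strong to call this a defect that undermines the study. No hypothesis is tested, safety data for approval are out of scope, the group is 15 of 50, and the main pre/post threshold comparison is in the newly implanted group (Section 11.0, item 1), which is followed after loss.

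**What to change.** **Protocol.** Reconcile Sections 6.0, 9.1, 9.2 and 9.4 so that existing-group participants who lose functional hearing remain in study follow-up to month 12, with at least unaided audiometry in both ears and adverse-event collection. Leave the device-return rule as it stands. Adjust the EAS-only testing instruction in Section 9.2 to match.

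**Analysis.** Add to Sections 10.0 and 11.0:

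- The denominator is all EAS-fitted existing participants.
- A loss of functional hearing counts as a loss at every later visit.
- Exit-visit thresholds are tabulated with the visit at which the loss was found.
- EAS-aided results at 12 months are labelled as conditional on retained hearing.

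**Cost.** The protocol change needs an amendment with consent revision and IRB review (Sections 14.3 and 14.4.1) and submission to FDA (Section 22.0), plus at most three extra visits per affected participant. The figures become slightly less favourable. The analysis rules need no extra data and would remove most of the bias in the retention counts even without the follow-up change, but they cannot supply the thresholds that were never measured.

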9.3 Unscheduled Visits

Unscheduled visits to the participant's managing implant center or physician may be made at any time for evaluation of possible adverse events or to address any questions or concerns expressed by the participant that cannot be managed adequately by telephone or e-mail communication. These visits are considered routine and standard of care.

9.4 Advanced Bionics Prototype Sound Processor Return and/or Retention

Study participants meeting the functional residual hearing in the implanted ear as defined within this study protocol, will retain use of the AB Prototype Sound Processor throughout the feasibility trial. Beyond the defined study endpoint (12 month test interval) participants (newly

implanted and existing implanted groups) fit with the AB Prototype Sound Processor have the option to retain the device until the time the AB commercial EAS device is released.

Newly implanted study participants not meeting the functional residual hearing criteria to be fit with the AB Prototype Sound Processor and/or who lose functional residual hearing post implant treatment (and fall outside the defined fitting criteria) during the 12 month test interval will return the prototype sound processor to Advanced Bionics. The participant maintains and/or resumes use of his/her AB commercial (owned) sound processor throughout the feasibility study and thereafter. Should existing group study participants lose acoustic residual hearing and fall outside the defined fitting criteria for the study during the 12 month test interval, the prototype EAS sound processor will be returned to Advanced Bionics.

10.0 Statistical Methods

General Considerations

Individual outcomes will be compared across pre- and postoperative test conditions for audiometric and speech performance outcomes. No formal statistical hypothesis will be tested. At a minimum, individual data/outcomes will be tabulated and summarized for audiometric and speech performance outcomes to establish numbers of subjects showing improvement, no change or decrease in performance. Descriptive statistics may consist of counts, means, median and standard deviations, percent and relative frequency for categorical variables (i.e. questionnaire). The proposed sample size the Sponsor is aiming to recruit for participation of 50 total subjects is deemed sufficient for determining the feasibility for the development of electric and acoustic stimulation technology.

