4.0 Purpose of the Investigation

The HiResolution™ Bionic Ear cochlear implant system is an implantable medical device system designed to provide individuals who have severe-to-profound hearing loss with access to sound and improved perception of speech via electrical stimulation of the hearing nerve. It consists of (1) an externally worn sound processor (2) internal implant device with receiver stimulator electronics package and electrode array, and (3) a custom fitting software used to program the external sound processor.

The purpose of the proposed feasibility study is to evaluate whether low-frequency acoustic hearing sensitivity can be preserved in newly implanted adults with partial deafness (considerable low frequency acoustic hearing profiles with severe-to-profound high frequency sensorineural hearing loss) using the HiResolution™ 90K™ Advantage cochlear implant with the HiFocus™ Mid-Scala electrode to support the development of electro-acoustic stimulation technology. A feasibility study approach will additionally provide basic, valuable aspects of device safety and functionality prior to an initiation of a pivotal study and aid to establish appropriate endpoints and outcome measures for such a study.

There are two groups of study participants that will be recruited for the feasibility study to support the development of electro-acoustic stimulation technology for a partial deafness population: a newly implanted group and an existing implanted group.

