7.3 Study Duration

The participant's study endpoint for the feasibility study is following completion of the twelve month test interval. It is expected that study participation for a subject enrolled in the feasibility study will involve a minimum 15-19 month commitment allowing for all scheduled test intervals and assessments.

The number of subjects proposed for recruitment in this feasibility study is estimated to be large enough to allow for trend analyses and to provide data suitable to support and complete product development.

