11.0 Efficacy Measures

An objective of the feasibility study is to facilitate and complete development of a combined input acoustic and electric stimulation (sound delivery) technology. Collection of efficacy data to support product approval is not part of this feasibility study. As such, no formal statistical hypothesis is being posed and/or applied. As part of this feasibility study, the following data will be collected and evaluated:

1. Postimplant audiometric hearing thresholds will be compared to preimplant thresholds in the newly implanted group to assess preservation of any low frequency acoustic residual hearing in the treated ear post intervention with the HiRes 90K™ Advantage cochlear implant with the HiFocus™ Mid-Scala electrode. Specifically, unaided pure tone hearing threshold measurement in the treated ear compared to preimplant audiometric thresholds (using a pure-tone average of .125, .25, .5 and 1 kHz for comparison) will be assessed. Individual and group comparisons will be made. Results will be tabulated and summarized based on pre- to postoperative change in pure-tone average (PTA).
2. Additionally, monosyllabic word recognition performance in quiet for the treated ear using the CNC word test and sentence recognition in noise using AzBio sentence test pre-to-post device activation will be compared, tabulated and summarized for the newly

implanted group. AzBio sentence understanding in noise pre-to-postoperatively will also be compared, tabulated and summarized in the bilateral listening condition. The intent of this individual and group comparison is to address the contribution and benefit of the implant treatment option in a partial deafness population as compared to the preimplant listening condition.

3. The Speech, Spatial Qualities (SSQ) and the Abbreviated Profile of Hearing Aid Benefit (APHAB) questionnaire score comparison pre-to-post device activation will be conducted (in the newly implanted group) to provide a subjective measure of patient perceived hearing performance/auditory benefit with this combined technology. The SSQ and APHAB will aid in providing a measure of subjective perceived benefit; individual and group comparisons will be made. Additional subjective data collected (i.e. Sponsor developed questionnaires) in the feasibility study will also be tabulated and summarized to evaluate amount of improvement, no change or decrement.

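### Section 7.3 justifies the sample size by trend analyses, but Sections 10 and 11 plan only pre-to-post changes and descriptive summaries, with no longitudinal analysis and no interval

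*Combined protocol and SAP*

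**What the plan says.** Section 7.3 supports the number of participants by describing it as "estimated to be large enough to allow for trend analyses and to provide data suitable to support and complete product development". Section 10 says that the sample "is deemed sufficient for determining the feasibility for the development of electric and acoustic stimulation technology". Neither gives a standard deviation, a rate or a precision target.

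Section 10 tests no hypothesis. It plans individual comparisons before and after surgery, and at least a count of participants who improve, stay the same or decline. It then says "Descriptive statistics may consist of counts, means, median and standard deviations, percent and relative frequency for categorical variables".

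Section 11, item 1, covers hearing thresholds in the newly implanted group: "Results will be tabulated and summarized based on pre- to postoperative change in pure-tone average (PTA"). Items 2 and 3 plan individual and group pre-to-post comparisons of speech scores and questionnaires, again for the newly implanted group. Item 4, which also covers the existing implanted group, says only that measures will be assessed and evaluated. Section 12.2 reports adverse events as number and percent.

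Section 4.0 says that the study will "aid to establish appropriate endpoints and outcome measures for such a study", meaning a later pivotal study.

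**The concern.** The design is repeated-measures with up to seven or eight threshold visits per newly implanted participant, and the sample size rests partly on trends. The plan never says how a trend will be estimated. The natural output of Sections 10 and 11 is a row of mean changes from baseline, one per visit, each computed on whoever was tested. Reading along that row is a trend only if the same ears contribute throughout.

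If ears with the larger losses drop out of the row, it shows less deterioration than occurred. Separately, a bare percentage from 35 or 15 ears looks firmer than it is, and these results are meant to inform the choice of pivotal endpoints.

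**Working it through.** **1. The plan's own figure.** Section 7.4: "Projected total study enrollment under this feasibility study is 50 subjects"; "thus 35 newly implanted subjects are to be recruited". The sum is 10 + 25 = 35 newly implanted, plus 15 existing implanted, giving 50. The total reproduces by addition. The claim that it suffices cannot be reproduced, because no formula input is given.

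**2. Where testing depends on hearing.**
- Section 8.3.1: after two consecutive visits with no measurable hearing, treated-ear unaided thresholds may be omitted (both groups).
- Section 9.2: an existing implanted participant who loses functional hearing leaves the study at that interval.
- Section 9.1: the 2-month visit is only for EAS-fitted participants, so that column covers a subset selected on hearing.
- Section 9.1: newly implanted participants are scheduled at 3, 6 and 12 months whether or not they qualify for EAS. Loss of hearing alone does not remove them.

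**3. Size of the effect by arithmetic.** Suppose k of n ears are untested at a visit, and their mean loss from baseline is d dB greater than that of the tested ears. Then

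mean loss in all = mean loss in tested + d × k/n,

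so the tabulated mean understates loss by d × k/n. The documents give neither k nor d, so both are assumed:

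| k/n | d = 10 dB | d = 20 dB | d = 30 dB |
|---|---|---|---|
| 3/15 = 0.20 | 2 dB | 4 dB | 6 dB |
| 7/35 = 0.20 | 2 dB | 4 dB | 6 dB |

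**4. Simulation of the planned summary.** Assumed: 35 ears; change from baseline with between-participant SD 15 dB and within-participant SD 5 dB; visits at 1, 3, 6 and 12 months; about 18% missing at month 12, with the chance of missing a visit rising with the last observed loss. The mean pre-to-post change in those tested at month 12 understates loss by about 3 dB. A mixed model using all visits is off by 0 to 0.4 dB. This agrees with step 3: 3 dB at 18% missing corresponds to d = 3/0.18, or about 17 dB.

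**5. Precision of proportions.** Exact (Clopper-Pearson) 95% intervals for illustrative counts:

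| Count | Percent | 95% interval |
|---|---|---|
| 25/35 | 71% | 54% to 85% |
| 28/35 | 80% | 63% to 92% |
| 12/15 | 80% | 52% to 96% |
| 0/35 | 0% | upper limit 10% |
| 0/15 | 0% | upper limit 22% |

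**6. Precision of a mean change.** The half-width is t × SD/√n. For assumed SDs of change of 10, 15 and 20 dB it is 3.4, 5.2 and 6.9 dB at n = 35, and 5.5, 8.3 and 11.1 dB at n = 15.

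**7. Speech scores.** The device worn at test changes with time: hearing aids before surgery, the commercial processor at month 1, EAS later if fitted, and the commercial processor again if hearing is lost (Section 9.1). A time trend without a device term would mix the two. At month 1, CNC in the treated ear and AzBio in the bilateral condition are tested with both processors, so device and time can be separated. Treated-ear AzBio is not. In the existing group it is measured with the commercial processor only at the first visit and with EAS only afterwards (Section 9.2).

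**The case against.** The strongest reply is that the plan already works within participants. Section 7.1 makes each participant the control, Section 10 opens with individual comparisons, and Section 11 summarises change in pure-tone average. A reader might infer from the list in Section 10 that only unpaired visit means are planned, with all the bias and loss of precision that this would bring. The documents do not support that: neither section limits the analysis to visit means, and both describe paired contrasts.

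This reply removes the charge of an unpaired analysis but not the point. Pairing with baseline does not fix which ears are in each column. A comparison of month 1 with month 12 in ears seen at both is nearly unbiased under similar assumptions, but the plan does not state that comparison.

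A second tempting inference is that newly implanted participants leave once hearing is lost. They do not. For them the documented routes are the threshold-stopping rule and the restricted 2-month visit, plus ordinary dropout of unknown size.

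It is also fair that this is a feasibility study, that efficacy and safety are to be proven elsewhere, and that the wording of Section 10 sets a floor which permits intervals. Section 4.0 speaks of endpoints and outcome measures; it does not say that observed rates will fix pivotal assumptions. The absence of a hypothesis test is a legitimate choice and is not criticised here.

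**Conclusion.** The point holds in a limited form. Trend analyses are used to justify the sample size, and the plan does not say how they will be done or how uncertainty will be shown. Outcome-related stopping is written into the protocol, fully for the 15 existing participants and only partly for the 35 newly implanted. In the larger group the bias of about 3 dB rests on assumed SDs and on 18% outcome-related missingness; with little such missingness it would be near zero. The interval widths need no such assumption beyond the illustrative counts. The plan is not invalid, and the remedy is a cheap improvement.

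**What to change.** Add to Section 10:

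1. **Treated-ear pure-tone average.** For each group, a descriptive linear mixed model using all available visits, with visit as a factor and participant as a random effect. Report the change at each visit (from the preoperative visit, or from the EAS fitting visit in the existing group) with a 95% confidence interval and the number tested. Score thresholds no longer tested under Section 8.3.1 as no response at the equipment limit, state that limit, and report how many ears are scored this way. Such scores are lower bounds on the loss.
2. **CNC and AzBio.** The same model, with the device worn at test (commercial or EAS) as a term. For treated-ear AzBio in the existing group, say that device and time cannot be separated and report their combined change.
3. **Proportions.** Exact 95% intervals for retention of functional hearing and for adverse-event rates. For retention, count participants whose testing or participation stopped because hearing was lost as not retained.
4. **Section 7.3.** Refer to item 1 as the meaning of trend analyses.

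The cost is plan wording and a few lines of code, with no new data and no hypothesis test. The drawbacks are visibly wide intervals and a model that assumes data are missing at random given the observed values. That is reasonable where exit follows a recorded threshold and less certain for ordinary dropout.
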